10.5.2.2. Handling of Partial Dates

Element	Reporting Detail
Concomitant Medications	
 Partial dates for any concomitant medications recorded in the eCRF will be imputed using the following convention: 
 If the partial date is a start date, a '01' will be used for the day and 'Jan' will be used for the month If the partial date is a stop date, a '28/29/30/31' will be used for the day (dependent on the month and year) and 'Dec' will be used for the month. The recorded partial date will be displayed in listings.
Adverse Events	
 Any partial dates for adverse events will be raised to data management. If the full date cannot be ascertained, the following assumptions will be made: 
 If the partial date is a start date, a '01' will be used for the day and 'Jan' will be used for the month. However, if these results in a date prior to Week 1 Day 1 and the event could possibly have occurred during treatment from the partial information, then the Week 1 Day 1 date will be assumed to be the start date. The AE will then be considered to start on-treatment (worst case). If the partial date is a stop date, a '28/29/30/31' will be used for the day (dependent on the month and year) and 'Dec' will be used for the month. The recorded partial date will be displayed in listings.

10.6. Appendix 6: Values of Potential Clinical Importance

10.6.1. ECG

ECG Parameter	Units	Potential Clinically Important Range	
		Lower	Upper
Absolute			
Absolute QTc Interval ^[3]	msec	> 450 ^[1]	
		> 450 ^[2]	≤ 479 ^[2]
		≥ 480 ^[2]	≤ 499 ^[2]
		≥ 500 ^[2]	
Absolute PR Interval	msec	< 110 ^[1]	> 220 ^[1]
Absolute QRS Interval	msec	< 75 ^[1]	> 110 ^[1]
Change from Baseline			
Increase from Baseline QTc ^[3]	msec	≤ 30 ^[2]	
	msec	> 30 ^[2]	≤ 59 ^[2]
	msec	≥ 60 ^[1]	

NOTES:

1. Represent standard ECG values of PCI for HV studies.
2. Represent further subdivisions of ECG values for analysis.
3. Qualifying QTc events, regardless whether QTcB or QTcF, will be captured.

10.6.2. Vital Signs

Vital Sign Parameter (Absolute)	Units	Potential Clinically Important Range	
		Lower	Upper
Systolic Blood Pressure	mmHg	< 85	> 160
Diastolic Blood Pressure	mmHg	< 45	> 100
Heart Rate	bpm	< 40	> 110

10.7. Appendix 7: Division of Microbiology and Infectious Disease Adult Toxicity Tables for Adverse Event Assessment

10.7.1. Laboratory Values

Parameter values are converted to use SI units.

HEMATOLOGY

	Grade 1	Grade 2	Grade 3	Grade 4
Hemoglobin	95 to 105 G/L	80 to 94 G/L	65 to 79 G/L	<65 G/L
Absolute neutrophil count	1.0 to 1.5 10 ⁹ /L	0.75 to 0.999 10 ⁹ /L	0.5 to 0.749 10 ⁹ /L	<0.5 10 ⁹ /L
Platelets	75 to 99.999 10 ⁹ /L	50 to 74.999 10 ⁹ /L	20 to 49.999 10 ⁹ /L	<20 10 ⁹ /L
White Blood Cells	11 to 13 10 ⁹ /L	13 to 15 10 ⁹ /L	15 to 30 10 ⁹ /L	>30 or <1 10 ⁹ /L
% Polymorphonuclear leukocytes + band cells	>80%	90 to 95%	>95%	N/A
Abnormal Fibrinogen	Low: 1 to 2 G/L High: 4 to 6 G/L	Low: <1 G/L High: >6 G/L	Low: <0.5 G/L High: N/A	Fibrinogen associated with gross bleeding or with disseminated coagulation
Fibrin Split Product	0.020 to 0.040 G/L	0.041 to 0.050 G/L	0.051 to 0.060 G/L	>0.060 G/L
Prothrombin Time	1.01 to 1.25 × ULN	1.26 to 1.5 × ULN	1.51 to 3.0 × ULN	>3 × ULN
Activated Partial Thromboplastin	1.01 to 1.66 × ULN	1.67 to 2.33 × ULN	2.34 to 3 × ULN	>3 × ULN
Methemoglobin	5.0 to 9.9%	10.0 to 14.9%	15.0 to 19.9%	>20%

N/A = not applicable; ULN = upper limit of normal.

CHEMISTRIES

	Grade 1	Grade 2	Grade 3	Grade 4
Hyponatremia	130 to 135 MMOL/L	123 to 129 MMOL/L	116 to 122 MMOL/L	<116 MMOL/L or abnormal sodium with mental status changes or seizures
Hypernatremia	146 to 150 MMOL/L	151 to 157 MMOL/L	158 to 165 MMOL/L	>165 MMOL/L or abnormal sodium with mental status changes or seizures
Hypokalemia	3.0 to 3.4 MMOL/L	2.5 to 2.9 MMOL/L	2.0 to 2.4 MMOL/L or intensive replacement therapy or hospitalization required	<2.0 MMOL/L or abnormal potassium with paresis, ileus, or life-threatening arrhythmia

	Grade 1	Grade 2	Grade 3	Grade 4
Hyperkalemia	5.6 to 6.0 MMOL/L	6.1 to 6.5 MMOL/L	6.6 to 7.0 MMOL/L	>7.0 MMOL/L or abnormal potassium with life-threatening arrhythmia
Hypoglycemia	3.0 to 3.55 MMOL/L	2.22 to 2.99 MMOL/L	1.67 to 2.21 MMOL/L	<1.67 MMOL/L or abnormal glucose with mental status changes or coma
Hyperglycemia (nonfasting and no prior diabetes)	6.44 to 8.88 MMOL/L	8.89 to 13.88 MMOL/L	13.89 to 27.75 MMOL/L	>27.76 MMOL/L or abnormal glucose with ketoacidosis or seizures
Hypocalcemia (corrected for albumin)	2.10 to 1.95 MMOL/L	1.94 to 1.75 MMOL/L	1.74 to 1.52 MMOL/L	<1.52 MMOL/L or abnormal calcium with life-threatening arrhythmia or tetany
Hypercalcemia (corrected for albumin)	2.64 to 2.87 MMOL/L	2.88 to 3.12	3.13 to 3.37 MMOL/L	>3.37 MMOL/L or abnormal calcium with life-threatening arrhythmia
Hypomagnesemia	0.7 to 0.6 MMOL/L	0.59 to 0.45 MMOL/L	0.44 to 0.3 MMOL/L	<0.3 MMOL/L or abnormal magnesium with life-threatening arrhythmia
Hypophosphatemia	0.7 to 0.8 MMOL/L	0.5 to 0.6 MMOL/L or replacement Rx required	0.3 to 0.4 MMOL/L intensive therapy or hospitalization required	<0.3 MMOL/L or abnormal phosphate with life-threatening arrhythmia
Hyperbilirubinemia (when accompanied by any increase in other liver function test)	1.1 to <1.25 × ULN	1.25 to <1.5 × ULN	1.5 to 1.75 × ULN	>1.75 × ULN
Hyperbilirubinemia (when other liver function tests are in the normal range)	1.1 to <1.5 × ULN	1.5 to <2.0 × ULN	2.0 to 3.0 × ULN	>3.0 × ULN
Blood urea nitrogen	1.25 to 2.5 × ULN	2.6 to 5 × ULN	5.1 to 10 × ULN	>10 × ULN
Hyperuricemia (uric acid)	446 to 595 UMOL/L	596 to 714 UMOL/L	715 to 892 UMOL/L	>892 UMOL/L
Creatinine	1.1 to 1.5 × ULN	1.6 to 3.0 × ULN	3.1 to 6.0 × ULN	>6 × ULN or dialysis required

Rx = therapy; ULN = upper limit of normal.

	Grade 1	Grade 2	Grade 3	Grade 4
ENZYMES				
	Grade 1	Grade 2	Grade 3	Grade 4
Aspartate aminotransferase	1.1 to <2.0 × ULN	2.0 to <3.0 × ULN	3.0 to 8.0 × ULN	>8.0 × ULN
Alanine aminotransferase	1.1 to <2.0 × ULN	2.0 to <3.0 × ULN	3.0 to 8.0 × ULN	>8.0 × ULN
Gamma to glutamyl transferase	1.1 to <2.0 × ULN	2.0 to <3.0 × ULN	3.0 to 8.0 × ULN	>8.0 × ULN
Alkaline Phosphatase	1.1 to <2.0 × ULN	2.0 to <3.0 × ULN	3.0 to 8.0 × ULN	>8.0 × ULN
Amylase	1.1 to 1.5 × ULN	1.6 to 2.0 × ULN	2.1 to 5.0 × ULN	>5.1 × ULN
Lipase	1.1 to 1.5 × ULN	1.6 to 2.0 × ULN	2.1 to 5.0 × ULN	>5.1 × ULN

ULN = upper limit of normal.

URINALYSIS				
	Grade 1	Grade 2	Grade 3	Grade 4
Proteinuria	1+ or 200 MG to 1 GM loss/day	2 to 3+ or 1 to 2 GM loss/day	4+ or 2 to 3.5 GM loss/day	Nephrotic syndrome or >3.5 GM loss/day
Hematuria	Microscopic only <10 RBC/HPF	Gross, no clots >10 RBC/HPF	Gross, with or without clots, or red blood cells casts	Obstructive or required transfusion

HPF = high-powered field; RBC = red blood cells.

10.8. Appendix 8: Multiple Comparisons & Multiplicity**10.8.1. Handling of Multiple Comparisons & Multiplicity**

No adjustments for multiplicity will be made.

10.9. Appendix 9: Model Checking and Diagnostics for Statistical Analyses.

10.9.1. Statistical Analysis Assumptions

Endpoint(s)	
• PK endpoints AUC(0-∞), AUC(0-t) and Cmax
Analysis	
• Mixed Effects

Assumptions:

- Model assumptions will be applied, but appropriate adjustments maybe made based on the data.
- The Kenward and Roger method for approximating the denominator degrees of freedom and correcting for bias in the estimated variance-covariance of the fixed effects will be used.

10.10. Appendix 10 - Abbreviations & Trade Marks

10.10.1. Abbreviations

Abbreviation	Description
AE	Adverse Event
Ae total	Total unchanged drug (total amount of drug excreted in urine)
Ae(t1-t2)	Amount of drug excreted in urine in a time interval
ANOVA	Analysis of variance
AUC(0-∞)	Area under the concentration-time curve from time zero (predose) extrapolated to infinite time
AUC(0-12)	Area under the urine concentration-time curve over time 0 (predose) to 12 hours after dosing.
AUC(0-24)	Area under the urine concentration-time curve over time 0 (predose) to 48 hours after dosing.
AUC(0-48)	Area under the urine concentration-time curve over time 0 (predose) to 48 hours after dosing.
AUC(0-t)	Area under the concentration-time curve from time zero (predose) to time of the last quantifiable concentration
BMI	Body mass index
CI	Confidence Interval
Cmax	Maximum observed concentration
CLr	Renal clearance of drug
CV	Coefficient of variance
DNAUC(0-t)	Dose normalized area under the concentration-time curve from time 0 (predose) to time of the last quantifiable concentration
DNAUC(0-∞)	Dose normalized area under the concentration-time curve from time 0 (predose) extrapolated to infinite time
DNCmax	Dose normalized maximum observed concentration
ECG	Electrocardiogram
eCRF	Electronic Case Report Form
fe%	Percentage of the given dose of drug excreted in urine
Frel	Relative bioavailability of drug
GSK	GlaxoSmithKline
hrs	Hours
HSWG	High shear wet granulation
IDSL	Integrated Data Standards Library
λz	Terminal phase rate constant
MedDRA	Medical Dictionary for Regulatory Activities
mg	Milligrams
msec	Milliseconds
%AUCex	The percentage of AUC (0-∞) obtained by extrapolation
PK	Pharmacokinetic

RAP	Reporting and Analysis Plan
RC	Related compound
SAE	Serious Adverse Event(s)
SAS	Statistical Analysis Software
SD	Standard Deviation
t _{1/2}	Terminal half-life
t _{lag}	Lag time before observation of drug concentrations in sampled matrix
Tmax	Time to first occurrence of C _{max}

10.10.2. Trademarks

Trademarks of the GlaxoSmithKline Group of Companies	Trademarks not owned by the GlaxoSmithKline Group of Companies
NONE	SAS WinNonlin

10.11. Appendix 11: List of Data Displays

10.11.1. Data Display Numbering

The following numbering will be applied for RAP generated displays:

Section	Tables	Figures
Study Population	1.1 to 1.8	
Safety	2.1 to 2.12	
Pharmacokinetic	3.1 to 3.12	3.1 to 3.7.2
Section	Listings	
ICH Listings	1 to 44	

10.11.2. Mock Example Referencing

Non IDSL specifications will be referenced as indicated and if required an example mock-up displays provided in [Appendix 11](#).

Section	Figure	Table	Listing
Study Population	POP_Fn	POP_Tn	POP_Ln
Safety	SAFE_Fn	SAFE_Tn	SAFE_Ln
Pharmacokinetic	PK_Fn	PK_Tn	PK_Ln

NOTES:

- Non-Standard displays are indicated in the 'IDSL / TST ID / Example Shell' or 'Programming Notes' column as '[Non-Standard] + Reference.'

10.11.3. Deliverable [Priority]

Delivery [Priority] ^[1]	Description
IA [X]	Interim Analysis
SAC [X]	Final Statistical Analysis Complete

NOTES:

- Indicates priority (i.e. order) in which displays will be generated for the reporting effort.

10.11.4. Study Population Tables

Study Population Tables					
No.	Population	IDSL / TST ID / Example Shell	Title	Programming Notes	Deliverable [Priority]
Subject Disposition and Analysis Sets					
1.1	Safety	NS1	Summary of Number of Subjects Enrolled by Country and Site ID		SAC [1]
1.2	Safety	ES1	Summary of Subject Disposition		SAC [1]
1.3	Screened	ES6	Summary of Reasons for Screening Failures		SAC [1]
1.4	Screened	DV1	Summary of Important Protocol Deviations		SAC [1]
Demographics and Baseline Characteristics					
1.5	Safety	DM3	Summary of Demographic Characteristics		SAC [1]
1.6	Safety	DM5	Summary of Race and Racial Combinations		SAC [1]
1.7	Safety	DM6	Summary of Race and Racial Combinations Details		SAC [1]
1.8	Safety	DM11	Summary of Age Ranges		SAC [1]

10.11.5. Safety Tables

Safety Tables					
No.	Population	IDSL / TST ID / Example Shell	Title	Programming Notes	Deliverable [Priority]
Adverse Events					
2.1	Safety	AE1	Summary of All Adverse Events		IA [1], SAC [1]
2.2	Safety	AE1	Summary of All Drug- Related Adverse Events		IA [1], SAC [1]
2.3	Safety	AE15	Summary of Common (>=25%) Non-serious Adverse Events by System Organ Class and Preferred Term (Number of Subjects and Occurrences)		IA [1], SAC [1]
2.4	Safety	AE16	Summary of Serious Adverse Events by System Organ Class and Preferred Term (Number of Subjects and Occurrences)		IA [1], SAC [1]
Laboratory Measurements					
2.5	Safety	LB1	Summary of Clinical Chemistry Change from Baseline		SAC [1]
2.6	Safety	LB1	Summary of Haematology Change from Baseline		SAC [1]
2.7	Safety	UR3b	Summary of Urinalysis Dipstick Results		SAC [1]
Electrocardiograms					
2.8	Safety	EG1	Summary of ECG Findings		SAC [1]
2.9	Safety	SAFE_T1	Summary of Frequency of Maximum Post-Dose ECG Parameter Corrected QTc Interval		SAC [1]
2.10	Safety	SAFE_T2	Summary of Frequency of Maximum Change from Baseline for ECG Parameter Corrected QTc Interval		SAC [1]
2.11	Safety	EG2	Summary of Change from Baseline in ECG Values		SAC [1]
Vital Signs					
2.12	Safety	VS1	Summary of Change from Baseline in Vital Signs		SAC [1]

10.11.6. Pharmacokinetic Tables

Pharmacokinetic Tables					
No.	Population	IDSL / TST ID / Example Shell	Title	Programming Notes	Deliverable [Priority]
PK Concentration Data					
3.1.1	PK	PK01	Summary of Plasma Gepotidacin Pharmacokinetic Concentration (ng/mL) - Time Data		IA [1], SAC [1]
3.1.2	PK	PK01	Summary of Plasma Gepotidacin Pharmacokinetic Concentration (ng/mL) - Time Data – Excluding Outliers	exclude outliers	SAC [1]
3.2	PK	PK01	Summary of Urine Gepotidacin Pharmacokinetic Concentration (ug/mL) - Time Data		SAC [1]
PK Derived Parameters					
3.3.1	PK	PKPT1	Summary Statistics of Derived Plasma Gepotidacin Pharmacokinetic Parameters	Parameters with units	IA [1], SAC [1]
3.3.2	PK	PKPT1	Summary Statistics of Derived Plasma Gepotidacin Pharmacokinetic Parameters – Excluding Outliers	Parameters with units, exclude outliers	SAC [1]
3.3.3	PK	PKPT1	Summary Statistics of Pooled Derived Plasma Gepotidacin Pharmacokinetic Parameters – Part 2 and 3	Parameters with units	SAC [1]
3.3.4	PK	PKPT1	Summary Statistics of Pooled Derived Plasma Gepotidacin Pharmacokinetic Parameters – Part 2 and 3 Excluding Outliers	Parameters with units, exclude outliers	SAC [1]
3.4	PK	PKPT1	Summary Statistics of Derived Urine Gepotidacin Pharmacokinetic Parameters	Parameters with units	SAC [1]

Pharmacokinetic Tables					
No.	Population	IDSL / TST ID / Example Shell	Title	Programming Notes	Deliverable [Priority]
3.5.1	PK	PKPT4	Summary Statistics of Log-Transformed Derived Plasma Gepotidacin Pharmacokinetic Parameters	Parameters with units	IA [1], SAC [1]
3.5.2	PK	PKPT4	Summary Statistics of Log-Transformed Derived Plasma Gepotidacin Pharmacokinetic Parameters – Excluding Outliers	Parameters with units, exclude outliers	SAC [1]
3.5.3	PK	PKPT4	Summary Statistics of Log-Transformed Pooled Derived Plasma Gepotidacin Pharmacokinetic Parameters – Part 2 and 3	Parameters with units	SAC [1]
3.5.4	PK	PKPT4	Summary Statistics of Log-Transformed Pooled Derived Plasma Gepotidacin Pharmacokinetic Parameters – Part 2 and 3 Excluding Outliers	Parameters with units, exclude outliers	SAC [1]
3.6	PK	PKPT4	Summary Statistics of Log-Transformed Derived Urine Gepotidacin Pharmacokinetic Parameters	Parameters with units	SAC [1]
PK Analysis Tables					
3.7	PK Parameter	PKPT3	Analysis of Plasma Gepotidacin Pharmacokinetic Parameters by Treatment	AUC(0-t), AUC(0-∞), Cmax only log-transformed	IA [1], SAC [1]
3.8	PK Parameter	PK_T1	Statistical Analysis of Plasma Gepotidacin Tmax by Treatment	Tmax Wilcox signed-rank test by group	IA [1], SAC [1]
3.9.1	PK Parameter	PKPT3	Analysis of Dose-Normalized Plasma Gepotidacin Pharmacokinetic Parameters for Fasted Japanese Subjects	DNAUC(0-t), DNAUC(0-∞), DNCmax only log-transformed by Treatment. Part 2 only.	SAC [1]
3.9.2	PK Parameter	PKPT3	Analysis of Dose-Normalized Plasma Gepotidacin Pharmacokinetic Parameters for Fasted Japanese Subjects – Excluding Outliers	DNAUC(0-t), DNAUC(0-∞), DNCmax only log-transformed by Treatment. Part 2 only, exclude outliers	SAC [1]

Pharmacokinetic Tables					
No.	Population	IDSL / TST ID / Example Shell	Title	Programming Notes	Deliverable [Priority]
3.9.3	PK Parameter	PKPT3	Analysis of Dose-Normalized Plasma Gepotidacin Pharmacokinetic Parameters for Pooled Japanese Subjects	DNAUC(0-t), DNAUC(0-∞), DNCmax only log-transformed by Treatment. Pooled Part 2 and 3 only	SAC [1]
3.9.4	PK Parameter	PKPT3	Analysis of Dose-Normalized Plasma Gepotidacin Pharmacokinetic Parameters for Pooled Japanese Subjects – Excluding Outliers	DNAUC(0-t), DNAUC(0-∞), DNCmax only log-transformed by Treatment. Pooled Part 2 and 3 only, exclude outliers	SAC [1]
3.10	PK Parameter	PKPT3	Analysis of Dose Proportionality of Plasma Gepotidacin Pharmacokinetic Parameters for Fed Japanese Subjects	AUC(0-t), AUC(0-∞), Cmax only log-transformed by Treatment. Part 3 only.	SAC [1]
3.11	PK Parameter	PK_T2	Outliers Identified Using Grubbs' Test on Gepotidacin Plasma Pharmacokinetic Parameters	AUC(0-t), AUC(0-∞), Cmax	SAC [1]

10.11.7. Pharmacokinetic Figures

Pharmacokinetic Figures					
No.	Population	IDSL / TST ID / Example Shell	Title	Programming Notes	Deliverable [Priority]
Individual Concentration Plots					
3.1	PK	PKCF1P	Individual Plasma Gepotidacin Concentration-Time Plots by Subject (Linear and Semi-Log)	Paginate by Subject	IA [1], SAC [1]
3.2	PK	PKCF1P	Individual Urine Gepotidacin Concentration-Time Plots by Subject (Linear and Semi-Log)	Paginate by Subject	IA [1], SAC [1]
Mean / Median Concentration Plots					
3.3.1	PK	PKCF2	Mean Plasma Gepotidacin Concentration-Time Plots by Treatment (Linear and Semi-log)	All treatments for each Part on one page	IA [1], SAC [1]
3.3.2	PK	PKCF2	Mean Plasma Gepotidacin Concentration-Time Plots by Treatment – Excluding Outliers (Linear and Semi-log)	All treatments for each Part on one page	SAC [1]
3.4	PK	PKCF2	Mean Urine Gepotidacin Concentration-Time Plots by Treatment (Linear and Semi-log)	All treatments for each Part on one page	SAC [1]
3.5.1	PK	PKCF3	Median Plasma Gepotidacin Concentration-Time Plots by Treatment (Linear and Semi-log)	All treatments for each Part on one page	IA [1], SAC [1]
3.5.2	PK	PKCF3	Median Plasma Gepotidacin Concentration-Time Plots by Treatment – Excluding Outliers (Linear and Semi-log)	All treatments for each Part on one page	SAC [1]
3.6	PK	PKCF3	Median Urine Gepotidacin Concentration-Time Plots by Treatment (Linear and Semi-log)	All treatments for each Part on one page	SAC [1]

Pharmacokinetic Figures					
No.	Population	IDSL / TST ID / Example Shell	Title	Programming Notes	Deliverable [Priority]
3.7.1	PK	PKPF3	Individual and Box plot of Dose-Normalized Gepotidacin Plasma Pharmacokinetic Parameters by Treatment	Present PK parameters for each dose level Pages: Part 2 (2 doses) in one page, Part 3 (3 doses) in one page, and Part 2 and 3 in one page (Part 2 1500 mg, Part 3 1500 mg, Part 2 3000 mg, and Part 3 3000 mg)	SAC [1]
3.7.2	PK	PKPF3	Individual and Box plot of Dose-Normalized Gepotidacin Plasma Pharmacokinetic Parameters by Treatment – Excluding Outliers	Present PK parameters for each dose level Pages: Part 2 (2 doses) in one page, Part 3 (3 doses) in one page, and Part 2 and 3 in one page (Part 2 1500 mg, Part 3 1500 mg, Part 2 3000 mg, and Part 3 3000 mg)	SAC [1]
3.7.3	PK	PKPF3	Individual and Box plot of Pooled Dose-Normalized Gepotidacin Plasma Pharmacokinetic Parameters by Treatment – Part 2 and 3	Present PK parameters for each dose level Pages: Pooled Part 2 and 3 DN parameters	SAC [1]
3.7.4	PK	PKPF3	Individual and Box plot of Pooled Dose-Normalized Gepotidacin Plasma Pharmacokinetic Parameters by Treatment – Part 2 and 3 Excluding Outliers	Present PK parameters for each dose level Pages: Pooled Part 2 and 3 DN parameters	SAC [1]

10.11.8. ICH Listings

ICH : Listings					
No.	Population	IDSL / TST ID / Example Shell	Title	Programming Notes	Deliverable [Priority]
Randomisation					
1	Safety	CP_TA1	Listing of Randomised and Actual Treatment		SAC [1]
Subject Disposition					
2	Safety	ES3	Listing of Reasons for Study Withdrawal		SAC [1]
3	Screened	ES7	Listing of Reasons for Screening Failure		SAC [1]
4	Screened	DV2	Listing of Important Protocol Deviations		SAC [1]
5	Safety	IE4	Listing of Subjects with Inclusion/Exclusion Criteria Deviations		SAC [1]
6	Safety	SP3	Listing of Subjects Excluded from Any Population		SAC [1]
Demographics					
7	Safety	DM4	Listing of Demographic Characteristics	Include height, weight and BMI	SAC [1]
8	Safety	DM10	Listing of Race		SAC [1]
Medical Conditions and Concomitant Medications					
9	Safety	MH3	Listing of Medical Conditions		SAC [1]
10	Safety	CM4	Listing of Concomitant Medications		SAC [1]
Exposure					
11	Safety	SAFE_L1	Listing of Exposure Data		SAC [1]

ICH : Listings					
No.	Population	IDSL / TST ID / Example Shell	Title	Programming Notes	Deliverable [Priority]
Safety					
12	Safety	AE2	Listing of Relationship Between System Organ Class and Verbatim Text		SAC[1]
13	Safety	AE7	Listing of Subject Numbers for Individual Adverse Events		SAC [1]
14	Safety	SAFE_L2	Listing of All Adverse Events		IA[1], SAC [1]
15	Safety	AE9CP	Listing of Study Drug Related Adverse Events		SAC [1]
16	Safety	AE9CP	Listing of Serious Adverse Events		SAC [1]
17	Safety	AE9CP	Listing of Adverse Events Leading to Withdrawal from Study		SAC [1]
18	Safety	SAFE_L3	Listing of Liver Adverse Events	Conditional display	SAC [1]
19	Safety	SAFE_L4	Listing of Cardiovascular Adverse Events	Conditional display	SAC [1]
20	Safety	SAFE_L5	Listing of Allergic Reaction Adverse Events	Conditional display	SAC [1]
21	Safety	SAFE_L6	Listing of Clostridium Difficile Testing	Conditional display	SAC [1]
22	Safety	SAFE_L7	Listing of Rash Events	Conditional display	SAC [1]
Laboratory Measurements					
23	Safety	LB6	Listing of Clinical Chemistry Toxicities of Grade 3 or Higher		SAC [1]
24	Safety	LB6	Listing of All Clinical Chemistry Data for Subjects with Toxicities of Grade 3 or Higher		SAC [1]
25	Safety	LB6	Listing of Haematology Toxicities of Grade 3 or Higher		SAC [1]
26	Safety	LB6	Listing of All Haematology Data for Subjects with Toxicities of Grade 3 or Higher		SAC [1]
27	Safety	UR2b	Listing of Urinalysis Toxicities of Grade 3 or Higher		SAC [1]
28	Safety	UR2b	Listing of All Urinalysis Data for Subjects with Toxicities of Grade 3 or Higher		SAC [1]

ICH : Listings					
No.	Population	IDSL / TST ID / Example Shell	Title	Programming Notes	Deliverable [Priority]
ECGs					
29	Safety	EG6	Listing of Abnormal ECG Findings		SAC [1]
30	Safety	EG6	Listing of All ECG Findings for Subjects with an Abnormal Finding		SAC [1]
31	Safety	EG4	Listing of ECG Values of Potential Clinical Importance		SAC [1]
32	Safety	EG4	Listing of All ECG Values for Subjects with Any Value of Potential Clinical Importance		SAC [1]
33	Safety	SAFE_L8	Listing of ECG Change from Baseline of Potential Clinical Importance		SAC [1]
Vital Signs					
34	Safety	VS5	Listing of Vital Signs of Potential Clinical Importance		SAC [1]
35	Safety	VS5	Listing of All Vital Signs for Subjects with Potential Clinical Importance Values		SAC [1]
Liver Events					
36	Safety	LIVER5	Listing of Liver Monitoring/Stopping Event Reporting	Conditional display	SAC [1]
37	Safety	MH3	Listing of Medical Conditions for Subjects with Liver Stopping Events	Conditional display	SAC [1]
38	Safety	SAFE_L10	Listing of Alcohol Intake at Onset of Liver Event	Conditional display	SAC [1]
39	Safety	PKCL1X	Listing of Plasma Concentration Data for Subjects with Liver Stopping Events	Conditional display	SAC [1]
40	Safety	LIVER7	Listing of Liver Biopsy Details	Conditional display	SAC [1]
41	Safety	LIVER8	Listing of Liver Imaging Details	Conditional display	SAC [1]

ICH : Listings					
No.	Population	IDSL / TST ID / Example Shell	Title	Programming Notes	Deliverable [Priority]
Pharmacokinetic					
42	PK	PKCL1X	Listing of Plasma Gepotidacin Concentrations (ng/mL) by Treatment	Please list all the concentration data including unscheduled. Repeat for all treatments and Part 2 if needed.	SAC [1]
43	PK	PKCL1X	Listing of Urine Gepotidacin Concentrations (ug/mL) by Treatment	Please list all the concentration data including unscheduled.	SAC [1]
44	PK Parameter	PKPL1P	Listing of Gepotidacin Plasma Pharmacokinetic Parameters by Treatment	Additional parameters include Frel (units) (B and C only), t _{1/2} (units) and tlag (units). Repeat for Treatment B and C. Repeat for Treatments D and E if needed.	SAC [1]

ICH : Listings					
No.	Population	IDSL / TST ID / Example Shell	Title	Programming Notes	Deliverable [Priority]
45	PK Parameter	PKPL1P	Listing of Gepotidacin Urine Pharmacokinetic Parameters by Treatment	Additional parameters include Ae(0-2) (units), Ae(2-4) (units), Ae(4-6) units, Ae(6-8) (units), Ae(8-12) (units), Ae(12-24) (units), Ae(24-36) (units), Ae(36-48) (units), AUC(0-12) (units), AUC(0-24) (units), AUC(0-48) (units). Repeat for Treatments B and C.	SAC [1]

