7.3.6. Clinical Safety Laboratory Assessments

All protocol-required laboratory assessments, as defined in [Table 10](#), must be conducted in accordance with the Laboratory Manual, and Protocol Time and Events Table ([Table 9](#)). Laboratory requisition forms must be completed and samples must be clearly labelled with the subject number, protocol number, site/center number, and visit date. Details for the preparation and shipment of samples will be provided by the laboratory and are detailed in the SRM. Reference ranges for all safety parameters will be provided to the site by the laboratory responsible for the assessments.

If additional non-protocol specified laboratory assessments are performed at the institution's local laboratory and result in a change in subject management or are considered clinically significant by the investigator (e.g., SAE or AE or dose modification) the results must be recorded in the eCRF.

Refer to the SRM for appropriate processing and handling of samples to avoid duplicate and/or additional blood draws.

Hematology, clinical chemistry, urinalysis and additional parameters to be tested are listed in [Table 10](#).

Table 10 Protocol-Required Safety Laboratory Assessments

Hematology			
Platelet count	RBC indices:	WBC count with differential:	
RBC count	MCV	Neutrophils	
Hemoglobin	MCH	Lymphocytes	
Hematocrit	MCHC	Monocytes	
		Eosinophils	
		Basophils	
Serum Chemistry^a			
Blood urea nitrogen	Potassium	Aspartate aminotransferase	Total and direct bilirubin
Creatinine	Sodium	Alanine aminotransferase	Total protein
Glucose	Calcium	Alkaline phosphatase	Albumin
Creatine kinase	Bicarbonate	Chloride	
Routine Urinalysis			
Specific gravity			
pH, glucose, protein, blood, and ketones by dipstick			
Microscopic examination (if blood or protein is abnormal)			
Other Screening Tests			
Hepatitis B surface antigen, hepatitis C antibody, and human immunodeficiency virus			
Follicle-stimulating hormone and estradiol (as needed in women of nonchildbearing potential only)			
Serum test for human chorionic gonadotropin (as needed in women of childbearing potential)			
Alcohol (via urine, blood alcohol, or breathalyzer test), cotinine, and drug screen (via serum, urine, or saliva) to include, at a minimum: amphetamines, barbiturates, cocaine, opiates, cannabinoids, and benzodiazepines).			
Fecal occult blood test and stool cultures as appropriate for gastrointestinal adverse events (Appendix 8)			

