9.4.2. Secondary Analyses

Safety Analyses

The following safety evaluations will be performed:

- Monitoring for AEs
- Changes in routine clinical laboratory parameters including serum chemistry, hematology, and urinalysis
- Clinically significant changes in vital sign measurements or physical examination findings
- Changes in 12-lead ECG measurements

Safety endpoints will include AEs, clinical laboratory results (serum chemistry [including liver function parameters], hematology, and urinalysis), vital sign measurements (systolic and diastolic blood pressure and heart rate), 12-lead ECG measurements, and physical examination findings.

All safety data will be presented in the data listings. Subject demographics, medical history, and prior and concomitant medications will be summarized by group using descriptive statistics. For continuous variables, these summaries will include sample size, mean, median, SD, minimum, and maximum.

For categorical variables, the summaries will include frequencies and corresponding percentages. No inferential hypothesis testing will be performed on the safety variables.

Adverse events will be coded using the MedDRA classification system.

Treatment-emergent AEs will be defined as any AEs, regardless of relationship to investigational product, that occur after the dose of investigational product. All AEs will be summarized by group at AE onset for the overall number of AEs and the percentage of subjects who experience them. The total number of AEs will be summarized by group and overall. Listings for the subsets of SAEs and treatment-related SAEs will be provided. The number of SAEs will be summarized. The incidence of AEs will also be summarized by system organ class and preferred term.

Clinical laboratory results, vital sign measurements (systolic and diastolic blood pressure and heart rate), and 12-lead ECG results will be summarized by change from baseline. Clinical laboratory values that are outside of the reference ranges will be flagged and evaluated for clinical significance by the investigator. Any ECG abnormalities, including but not limited to a QTc >500 msec or increase in QTc from the baseline ECG of ≥ 60 msec, will be summarized by group.

Detailed descriptions of the analyses in this study will be presented in the RAP.

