10.4. Appendix 4: Derived and Transformed Data

10.4.1. General

Multiple Measurements at One Time Point

 Mean of the measurements will be calculated and used in any derivation of summary statistics but if listed, all data will be presented. If there are two values within a time window the value closest to the target day for that window will be used. If values are the same distance from the target then the mean will be taken. Subjects having both High and Low values for Normal Ranges at any post-baseline visits for safety parameters will be counted in both the High and Low categories of “Any visit post-baseline” row of related summary tables. This will also be applicable to relevant Potential Clinical Importance summary tables.
Study Day

 Calculated as the number of days from randomisation date: 
 Ref Date = Missing → Study Day = Missing Ref Date < Randomisation Date → Study Day = Ref Date – Randomisation Date Ref Date ≥ Randomisation Date → Study Day = Ref Date – (Randomisation Date) + 1

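### SAP Listings 23 to 28 show laboratory data only where a DMID Grade 3 or higher value occurs, while the protocol promises to list all safety data and flag out-of-range values; the SAP does not declare the restriction

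*SAP*

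**What the plan says.** Protocol 9.4.2 makes two commitments about individual laboratory results, neither with a severity threshold: "All safety data will be presented in the data listings", and "Clinical laboratory values that are outside of the reference ranges will be flagged and evaluated for clinical significance by the investigator".

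SAP 10.11.8 plans six routine laboratory listings, in three pairs. The first of each pair shows the Grade 3 or higher values. The second shows the whole panel, but only for subjects with such a value: "Listing of All Clinical Chemistry Data for Subjects with Toxicities of Grade 3 or Higher" (Listing 24), "Listing of All Haematology Data for Subjects with Toxicities of Grade 3 or Higher" (Listing 26) and "Listing of All Urinalysis Data for Subjects with Toxicities of Grade 3 or Higher" (Listing 28). The laboratory tables in SAP 10.11.5 are change from baseline for chemistry and hematology (Tables 2.5 and 2.6) and dipstick results (Table 2.7).

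Other SAP text points away from a restriction:
- SAP Table 8 marks individual listings for chemistry, hematology and urinalysis with no grade condition, though it refers to Appendix 11 for details.
- SAP 10.3.3 keeps unscheduled visits out of tables and figures and sends all of them to the listings.
- SAP 10.4.1 gives a counting rule for a normal-range table: "Subjects having both High and Low values for Normal Ranges at any post-baseline visits for safety parameters will be counted in both" the High and the Low category. No table in Appendix 11 has those categories.
- SAP 2.1 declares a single change from the protocol's analysis, the Part 3 power model.

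**The concern.** The protocol defines what must be visible by the reference range; Appendix 11 defines it by a severity grade. The two differ by everything graded 1 or 2 and by every analyte that the grading table omits. Clinical laboratory data are a secondary endpoint in every part, and Parts 2 and 3 have only about 10 subjects on active drug each. In groups that small, a laboratory signal is found mainly by looking at individual subjects, and the plan withholds those data unless a severe value occurs. A reader of the study report could not see which values were out of range, judged not clinically significant and set aside.

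**Working it through.** The documents state no figure on this point. The check sets the texts side by side and counts what the Grade 3 trigger can reach.

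**1. Analytes.** The measured analytes are those in Protocol Table 10 (7.3.6). Its hematology block includes "WBC count with differential", with five cell types; its chemistry block includes "Total and direct bilirubin", counted here as two. Each was matched to a graded row in SAP Appendix 7.

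| Panel | Measured | Graded | No grade |
|---|---|---|---|
| Hematology | 13 | 4 (hemoglobin, neutrophils, platelets, white cells) | 9 (red cells, hematocrit, MCV, MCH, MCHC, lymphocytes, monocytes, eosinophils, basophils) |
| Chemistry | 16 | 10 (sodium, potassium, glucose, calcium, total bilirubin, urea nitrogen, creatinine, AST, ALT, alkaline phosphatase) | 6 (creatine kinase, bicarbonate, chloride, direct bilirubin, total protein, albumin) |
| Urinalysis | 6 | 2 (protein, blood) | 4 (specific gravity, pH, glucose, ketones) |

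Hematology plus chemistry: 9 + 6 = 15 ungraded of 13 + 16 = 29. With urinalysis: 15 + 4 = 19 of 29 + 6 = 35. Counting bilirubin once gives 14 of 28, or 18 of 34 with urinalysis.

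**2. Graded analytes below the trigger.** In SAP Appendix 7 these are all Grade 2 and alone trigger no listing: creatinine up to 3.0 x ULN, ALT just under 3.0 x ULN, potassium 2.5 to 2.9 mmol/L, platelets 50 to 74.999 x 10^9/L. Grade 3 for ALT starts at 3.0 x ULN, the level of the liver stopping criterion in Protocol 5.4.1. Low white cells are graded only below 1 x 10^9/L.

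**3. What the change tables show.** In a group of 10, one subject whose ALT rises from 0.5 to 2.9 x ULN moves the mean change by (2.9 - 0.5)/10 = 0.24 x ULN. A minimum, maximum and SD would hint at such a value, but a summary does not identify the subject.

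**4. Unscheduled results.** SAP 10.3.3 excludes them from tables and figures. Listings 23 to 28 exclude them unless the subject has a Grade 3 or higher value in that panel. An unscheduled result from any other subject therefore appears in no routine laboratory display. Such results are foreseeable, because Protocol 7.3.6 asks for clinically significant abnormal values to be repeated.

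**The case against.** The strongest reply is that the investigator's review remains in place. The protocol's flag is a step for the investigator, and nothing in the SAP cancels it. Under Protocol Appendix 5 a laboratory abnormality judged clinically significant is an adverse event, and the SAP tabulates adverse events and lists them all (Listing 14). This stands, and it rules out two inferences a reader might draw: that sub-Grade 3 values are never flagged, and that the trial could report no laboratory findings despite clinically significant ones. It does not close the gap. The protocol promises both a flag and an evaluation, and the planned displays are specified to show only abnormalities that the evaluation turned into adverse events.

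A reader might also infer that the 15 ungraded analytes never appear. They do: in Tables 2.5 and 2.6, and in Listings 24 and 26 for a subject with a Grade 3 or higher value in the same panel. Protocol Appendix 6 also has a general severity scale for parameters outside its tables. SAP Appendix 7 does not reproduce it, so whether it could feed these listings is unstated. The LB1, LB6 and UR2b shells are not in the documents, so whether they print range flags cannot be checked.

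Finally, Protocol 9.4.2 asks for laboratory summaries by change from baseline, which Tables 2.5 and 2.6 provide. It does not require a shift table, and the SAP 10.4.1 rule may be leftover template text. The ECG and vital-sign listings are also restricted, but Tables 2.9 and 2.10 already categorize QTc, and the SAP's categories start at QTc above 450 msec. Those points are secondary.

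**Conclusion.** The discrepancy between protocol and SAP is real and undeclared, and the SAP is also inconsistent with itself. Followed as written, Listings 23 to 28 contain nothing for a subject whose laboratory changes are all Grade 1 or 2. Fifteen of 29 hematology and chemistry analytes (19 of 35 with urinalysis) have no grade in SAP Appendix 7 that could trigger a listing. No planned display is specified to identify out-of-range values that were not reported as adverse events.

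This weakens the reporting of a secondary safety endpoint and should be corrected. It does not touch the pharmacokinetic results, and no data are lost, because the values are collected and analysis datasets are built. The conclusion takes Appendix 11 as the governing list of displays, as SAP Table 8 indicates. The clinical values in the working illustrate what the rule misses; they do not predict what will occur.

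**What to change.** In SAP 10.11.8, replace the Grade 3 trigger in Listings 23 to 28 with listings of all chemistry, hematology and urinalysis data for the Safety Population, including unscheduled results. Add high/low reference-range flags, and the DMID grade where one exists. The Grade 3 or higher listings can stay as subsets. If the restriction is intended, SAP 2.1 should declare and justify it, and SAP Table 8 and 10.3.3 should be brought into line.

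Two additions are optional: one table counting subjects with out-of-range values by part and treatment, using the SAP 10.4.1 rule; and complete ECG and vital-sign listings, to match Protocol 9.4.2.

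The cost is SAP wording and unrestricted versions of listings already planned. No new data are needed. The listings become longer, but the planned numbers are small: about 27 + 10 + 12 = 49 subjects in Parts 1a, 2 and 3, since Protocol 9.3.2 says Part 1b is no longer needed.
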